### 1.0 Objectives

- 1.1. This project is intended to evaluate an educational website, thepainlesspush.com, especially with respect to its influence on parturients' satisfaction with particular aspects of the delivery process.
- 1.2. The investigators hypothesize that parturients with access to the website will exhibit greater satisfaction.

#### 2.0 Background

- 2.1 Prior studies have shown variance in overall satisfaction scores for labor and delivery regardless of analgesic approach, implicating that multiple factors other than pain relief alone are involved in the childbirth experience. (1-3)
- 2.2 No preliminary data have been obtained. The investigators created the website under review, and intend to test its effect on patient satisfaction.

#### 3.0 Inclusion and Exclusion Criteria

- 3.1. All patients who are admitted to the UMNH Labor and Delivery Floor and will be progressing to active labor during that admission will be considered for eligibility. As part of standard practice, anesthesiology is knowledgeable about patients who are likely to progress to active labor and delivery. These patients will be considered eligible and offered enrollment into the study.
- 3.2. All English- or Spanish-speaking pregnant patients who are admitted to UNMH Labor and Delivery for planned progression to active labor will be eligible for inclusion. All pregnant patients will be eligible, no matter what gestational age, how many previous deliveries, or planned induction. Exclusions include age under 18 years, those unable to provide consent for medical procedures, and women who do not speak either English or Spanish.
- 3.3. Special populations:
  - Adults unable to consent: Excluded
  - Individuals who are not yet adults (infants, children, teenagers): Excluded
  - Pregnant women: Included
  - Prisoners: Excluded
- 3.4. No particular racial or ethnic group will be excluded.

# 4.0 Study-Wide Number of Subjects

- 4.1. This is not a multicenter study.
- 4.2. The investigators plan to recruit up to 150 patients. The target sample size after attrition is approximately 100 completed surveys, but if actual attrition is less than anticipated, data may be obtained on up to 150 participants.

Page 2 of 10 Template: 7/1/2015

4.3. The target sample size should be sufficient at  $\alpha$ =0.05 and 80% power to detect a difference between group means equal to approximately 58% of the standard deviation.

#### 5.0 Study-Wide Recruitment Methods

This is not a multicenter study.

#### 6.0 Multi-Site Research

6.1 NA; this is not multi-site research.

## 7.0 Study Timelines

7.1 The duration for an individual's active participation in the research will be from the time they sign the consent form until after they have delivered their baby and completed the satisfaction survey.

Depending on speed of labor progression and the delivery, this could be hours or days. The investigators anticipate that enrollment will take approximately six months, with another six months for data analysis.

## 8.0 Study Endpoints

- 8.1 Enrollment will terminate upon completion of the intended sample size.
- 8.2 The investigators have not identified any safety or exploratory endpoints.

#### 9.0 Procedures Involved\*

- 9.1 This is a prospective randomized study of an educational website.
- 9.2 Potential participants will be offered participation in the study. If they choose to participate, they will be enrolled following the consent process. They will be randomized into either control group or intervention group. Control group participants will receive usual care and routine hospital pain-relief information. Intervention group participants will receive usual care, plus one hour in which to view the patient education website thepainlesspush.com, on an iPad provided by the Anesthesiology department for this purpose. After their delivery and transfer to the mother/baby unit, participants will complete a satisfaction survey brought to them by a study team member. Participants will complete the survey following their delivery and prior to discharge. Their active participation in the study will be complete at this time.
- 9.3 After a participant completes the satisfaction survey, research team members will collect demographic information and relevant obstetric/medical history information from the electronic medical record.

# 10.0 Data and Specimen Banking

Page 3 of 10 Template: 7/1/2015

10.1 Identifiable data will not be banked for future use. Deidentified data may be retained indefinitely for use as pilot data for future studies. Any such future study would only proceed with separate HRRC approval.

#### 11.0 Data and Specimen Management

- 11.1 Demographic and medical-history data will be described with routine descriptive statistics. Survey data will be reported with appropriate crosstabulations. The two study arms will be compared on the survey questions with routine Wilcoxon-Mann-Whitney test.
- 11.2 The target sample size should yield sufficient power at  $\alpha$ =0.05 and 80% power to detect a difference between group means equal to approximately 58% of the standard deviation.
- 11.3 All study team personnel carry all appropriate HIPAA and HITECH certifications as required by UNM HSC, as well as CITI human-subjects research certification. Data forms will be kept only temporarily, until deidentified data are entered onto a spreadsheet stored on secure UNM HSC servers. Temporary usage of identifiers is necessary in order to permit accurate linkage of survey responses to arm assignment and electronic medical record information. Investigators may notify one another of recent enrollments by use of the \*secure\* function in UNM Health Sciences Center email or the TigerConnect communication system, both of which are HIPAA-compliant and appropriate for internal exchange of PHI according to the UNM Health System IT Security group and the HSC Chief Information Officer. Remaining study records will be maintained for at least 3 years after study closure.
- 11.4 A separate linking document will be used to link identifiers (medical record number) to study ID numbers. This document will be kept separately from study data, in a locked cabinet in an Anesthesiology Department office belonging to a study team member. Only study team members will have access to the linking document. It will be securely maintained until data collection is complete (up to approximately one year), at which point it will be securely shredded. The destruction of that linking document will deidentify the study data.

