### 13.0 Withdrawal of Subjects

- 13.1 The investigators have not identified any circumstances in which a participant may be withdrawn without their consent.
- 13.2 If any participants withdraw from the research, investigators will simply stop collecting data on them. Participants who do not with so continue participating may also elect to simply stop providing answers on the post-delivery survey.

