#### **26.0** Consent Process

26.1 Consent will be obtained prior to enrollment. The investigators are requesting waiver of documentation of consent and HIPAA authorization, and use of an oral process for both consent and HIPAA authorization. As noted above, the research presents no more than minimal risk of harm to subjects. Similarly, it is routine to provide information on analgesia options and consultation to laboring women at UNMH. The educational website being evaluated is merely a specific option within the available educational materials. Healthcare satisfaction surveys (such as the Press Ganey healthcare satisfaction survey) are regularly conducted without formal written consent. For those reasons, the investigators believe that this project involves no procedures for which written consent is normally required outside the research context. The demographic and health information to be used in this study will be obtained from the electronic medical record by authorized personnel, and identifiers will be kept only temporarily. A script for an oral consent and

Page 8 of 10 Template: 7/1/2015

HIPAA authorization process is included with this application, along with a post-participation informational handout. The oral consent/HIPAA script includes the usual elements of consent, as well as listing the PHI to be used for the study, referencing HIPAA and the requirement that patients give permission for use of PHI, and specifically asking for permission to "let us use your protected information."

- The consent process will occur in regular patient rooms on the UNMH Labor/Delivery floor, which are already sufficiently private for appropriately confidential doctor/patient conversations.
- The investigators believe that avoiding the requirement for prospective participants to read, comprehend, and sign a complicated consent/HIPAA document while in labor will better respect their privacy considerations. An oral process will be considerably less intrusive, while respecting patient autonomy and addressing all other required elements of consent and HIPAA authorization.
- Patients will be free to read the educational materials, or not, as they see fit; similarly, they can choose to decline to answer any or all of the satisfaction-survey questions. The investigators do not anticipate that ongoing consent will become an issue.

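### Several survey questions are tested for one hypothesis of greater satisfaction, but no question or score is named to decide it, and the power statement is tied to no variable

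*Combined protocol and SAP*

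**What the plan says.** The objective in 1.1 is the website's influence on "satisfaction with particular aspects of the delivery process"; the aspects are not listed. Section 1.2 then states one directional hypothesis: "The investigators hypothesize that parturients with access to the website will exhibit greater satisfaction".

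Section 8.0, Study Endpoints, contains a recruitment stop ("Enrollment will terminate upon completion of the intended sample size") and a sentence saying that no safety or exploratory endpoints were identified. It names no satisfaction outcome.

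The analysis is one sentence in 11.1: "The two study arms will be compared on the survey questions with routine Wilcoxon-Mann-Whitney test". That there is more than one question is confirmed in 26.1, where participants are told that "they can choose to decline to answer any or all of the satisfaction-survey questions". Section 13.2 likewise says that those who do not wish to continue "may also elect to simply stop providing answers on the post-delivery survey". No rule for unanswered questions is given.

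On size, 4.2 says: "The target sample size after attrition is approximately 100 completed surveys", with recruitment of up to 150. Sections 4.3 and 11.2 both claim, at α = 0.05, "80% power to detect a difference between group means equal to approximately 58% of the standard deviation". Neither says which variable's standard deviation is meant. These two sections are the only places where a significance level appears.

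**The concern.** There is one hypothesis and an unspecified number of tests, with nothing to connect them. If the arms differ on one question and not on the others, the plan does not say whether 1.2 has been supported. That decision could be taken after the results are seen, for a website that the investigators themselves created (2.2).

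Two things are at stake. First, if any significant question may count, the false-positive rate for 1.2 exceeds the single-test rate whenever there are two or more imperfectly correlated questions. Second, the power statement describes one comparison. With no comparison named, it cannot be checked against an outcome, and about 100 returned surveys need not mean about 100 answers to the question that matters.

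**Working it through.** **Step 1. Reproduce the plan's power figure.** Inputs from the documents: about 100 completed surveys (4.2), α = 0.05, 80% power, 0.58 SD (4.3, 11.2), Wilcoxon-Mann-Whitney test (11.1). Assumed, because not stated: 1:1 allocation, so 50 per arm; a two-sided test; roughly normal data.

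Method: two-sample t-test power (noncentral t), with the per-arm size multiplied by the Wilcoxon efficiency 3/π.

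- Effective size per arm: 50 × 3/π = 47.75
- Degrees of freedom: 2 × 47.75 − 2 = 93.5, critical value 1.986
- Noncentrality: 0.58 × √(47.75/2) = 2.834
- Power: 80.1%; difference detectable with 80% power: 0.579 SD

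The figure reproduces. At one-sided 0.05 the detectable difference would be 0.513 SD, so 58% matches a two-sided test. The match is for one comparison. On 5-point items it is only approximate: simulated power at 0.58 pooled SD was 80.8% to 84.1% over three response distributions, and 88.0% when 70% of controls give the top score.

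**Step 2. Look for the rule that decides 1.2.** Section 1.2 gives a single claim, 8.0 names no satisfaction outcome, 11.1 tests questions in the plural, and 4.3 and 11.2 name no variable. No section supplies a primary question or score, a testing order, an adjustment or a success criterion.

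**Step 3. Size the consequence under a stated assumption.** Suppose any significant question could be read as supporting 1.2. Take k questions, each tested at two-sided 0.05, with equicorrelated normal test statistics of correlation ρ. With φ and Φ the standard normal density and distribution function and c = 1.96:

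- At least one false result favouring the website: 1 − ∫ φ(z) [Φ((c − √ρ z)/√(1 − ρ))]^k dz
- At least one false result in either direction: the same, with the bracket replaced by Φ((c − √ρ z)/√(1 − ρ)) − Φ((−c − √ρ z)/√(1 − ρ))

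| k (assumed) | Favouring website, ρ 0.7 to 0.5 | Favouring website, ρ = 0.9 | Either direction, ρ 0.7 to 0.5 |
|---|---|---|---|
| 1 | 2.5% | 2.5% | 5% |
| 2 | 4.2–4.5% | 3.5% | 8.3–9.1% |
| 3 | 5.5–6.3% | 4.2% | 10.9–12.5% |
| 5 | 7.4–9.1% | 5.1% | 14.8–18.3% |
| 10 | 10.7–14.4% | 6.4% | 21.3–28.7% |

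The website-favouring columns are the relevant ones, because 1.2 claims greater satisfaction and a result favouring control cannot support it.

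**Step 4. Skipped questions.** With the Step 1 method, if an assumed 10% or 20% of 100 respondents skip the deciding question, 45 or 40 per arm remain. Power at 0.58 SD is then 75.7% or 70.6%, and the detectable difference 0.61 or 0.65 SD. If collection instead runs to the ceiling of 150 (75 per arm) and 20% skip, 60 per arm remain and power is 86.8%.

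**Step 5. Why one primary outcome rather than a split alpha.** If all k questions stayed confirmatory under Bonferroni at 50 per arm, power at 0.58 SD on one question would be 71.0% (k = 2), 58.2% (k = 5) or 48.7% (k = 10). With one primary outcome at two-sided 0.05 it stays at 80.1%.

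**The case against.** The strongest reply is that the plan never says that each question is a confirmatory test at 0.05, or that one significant question would establish 1.2. This is correct. The level appears only in the power statements; applying it to each question is the natural reading, not a stated testing rule. The inflated error rate is therefore conditional. The missing deciding outcome is not.

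Second, the survey form is not in the text reviewed, so the number of items is unknown and the form may define a total score. That also stands, and it is why every rate above rests on assumption. But 11.1 tests questions and designates no score, so a total on the form would not by itself decide 1.2.

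Third, skipping is a lesser issue: the rates are assumed, and the ceiling of 150 can absorb them.

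A reader might also infer more than the documents support:

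- *Selective reporting is planned.* It is not; 11.1 can be read as reporting every comparison.
- *The title and 1.1 name competing outcomes.* The title speaks of satisfaction with pain relief, but pain relief can be one of the aspects in 1.1.
- *The false-positive risk for 1.2 is the 21.3–28.7% shown for 10 questions.* About half of that is results favouring control.
- *The sample size is wrong.* It reproduces for one comparison.

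**Conclusion.** The point holds as a gap in the decision rule, and it should be fixed. Run as written, 11.1 produces several unadjusted tests for one hypothesis and leaves open until the results are seen which of them decides it. The power calculation is sound but belongs to no named outcome.

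The omission is certain from the text; its numerical size is not. If any significant question could count, the chance of a false result favouring the website is between about 1.7 times (4.2/2.5, 2 questions, ρ = 0.7) and 5.8 times (14.4/2.5, 10 questions, ρ = 0.5) the 2.5% for a single test. This assumes two-sided 0.05 tests; the number of questions and the correlation are also assumed. At ρ = 0.9 the excess is smaller but does not vanish.

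**What to change.** Before any survey responses are compared by arm:

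- **8.0:** name one primary outcome, chosen by the investigators to match 1.1. It may be a single item or a prespecified summary score. A summary score needs a rule for skipped items: the instrument's own if it has one, otherwise, for example, the mean of answered items when at least half are answered.
- **11.1:** test that outcome once at two-sided 0.05 and report usable responses per arm. Make the other questions secondary, either Holm-adjusted or given as estimates with 95% confidence intervals and no confirmatory claim.
- **4.3 and 11.2:** state that the 0.58 SD figure refers to that outcome, assumes about 100 usable responses to it, and is approximate.
- **4.2 and 22.2 (optional):** count the target of about 100 as usable responses to the primary outcome.

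The cost is wording. If some participants skip the primary item, a few more surveys may be needed, within the existing ceiling of 150. The real downside is that a significant result on a non-primary question can no longer be claimed as confirming 1.2.

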## 12.0 Provisions to Monitor the Data to Ensure the Safety of Subjects

This study consists of exposure to an educational website, a satisfaction survey, and correlation of survey responses to arm assignment and basic demographic/medical information. The primary risk is confidentiality breach (see section 14 below). Identifiers will only be kept temporarily, and this study does not involve data typically seen as "sensitive." The investigators thus believe that this study poses no more than minimal risk.

Page 4 of 10 Template: 7/1/2015

### 13.0 Withdrawal of Subjects

- 13.1 The investigators have not identified any circumstances in which a participant may be withdrawn without their consent.
- 13.2 If any participants withdraw from the research, investigators will simply stop collecting data on them. Participants who do not with so continue participating may also elect to simply stop providing answers on the post-delivery survey.

#### 14.0 Risks to Subjects

- 14.1 The only difference between study arms is the availability of an educational website. Therefore, the primary risk relates to potential loss of confidentiality. A reduced dataset of demographic and health-related information will be gathered to better understand patterns in the post-delivery satisfaction survey data. Similarly, identifiers will only be kept temporarily in order to accurately link arm assignment, demographic/health data, and satisfaction survey responses.
- 14.2 The investigators do not believe that the study procedures may reasonably be said to carry substantial unforeseeable risks: the study consists of access to an educational website (or routine information) and a satisfaction survey.
- 14.3 All subjects will be pregnant at the time of enrollment, but the investigators have not identified any risks to the fetus arising from reading an educational website. This project does not propose to modify any clinical decisions made by parturients, physicians, nurses, or midwives. The remaining study procedure, completing a satisfaction survey, occurs after delivery.
- 14.4 The investigators have not identified any risks to others arising from subjects' participation in this study.

## 15.0 Potential Benefits to Subjects

15.1 The main potential benefit that participants may experience would be an increased knowledge base and understanding of pain relief options during labor and delivery. This may help them feel more prepared for delivery and more comfortable with their various pain relief options. This knowledge may also be useful for any future pregnancies or deliveries.

# **16.0** Vulnerable Populations

16.1 The study targets pregnant women, but no other vulnerable group (prisoners, students, economically disadvantaged, etc). Pregnant women are regularly seen for labor and delivery at UNM Hospital. [name] regularly treats laboring women as part of her routine clinical duties. This study does not modify any clinical decisions.

Page 5 of 10 Template: 7/1/2015

As noted elsewhere, the only intervention is the selection of painrelief educational materials: the existing materials in routine use, or the newly-developed website. The study thus presents minimal risk.

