#### 21.0 Recruitment Methods

- 21.1 Patients will be recruited following admission to the UNMH Labor & Delivery floor for expected delivery.
- 21.2 UNMH serves a large catchment area, and expectant mothers present daily for labor and delivery.
- 21.3 Physicians on the Obstetrics service routinely notify Anesthesiology of parturients expected to progress to active labor, in order for them to provide possible consultation and appropriate pain relief care. The study team will identify potential participants from among this patient population. Anesthesiology providers regularly review the medical records of this patient population upon receiving this notification, for purposes of clinical treatment. The investigators are requesting a partial waiver of HIPAA authorization requirements in order to permit the use of a subset of these records for purposes of verifying eligibility (i.e. that potential participants do not meet the few exclusion criteria). The research-related protected health information will not be reused or disclosed to any other person or entity, except as required by law, for authorized oversight of the research study, or for other research for which the use or disclosure of protected health information for which an opportunity to agree or object is not required by 45 CFR 164.512.
- 21.4 Recruitment will occur in person, and will not involve audio or video materials.
- 21.5 A recruitment flyer will be posted in patient areas of the Labor & Delivery floor, and copies of it may be distributed to potential participants.
- 21.6 Participants will not be paid.

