#### 23.0 Provisions to Protect the Privacy Interests of Subjects

- 23.1 Investigators who will conduct recruitment and consent are already authorized for patient contact in this situation, so recruitment will not involve any extraneous or unexpected personnel.
- 23.2 Investigators are already experienced at interacting with patients during a time that is stressful in general (i.e. labor) and at specific moments during that time (i.e. between contractions). Recruitment and consent efforts will not interfere with these interactions, or be "forced" during contractions.
- 23.3 The PI is already authorized to contact these patients and review their records as part of medical practice.
- 23.4 The post-delivery satisfaction survey will occur in the Mother/Baby Unit prior to discharge, in order to provide some opportunity to recover from the stress of delivery.

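### No step keeps the arm from clinicians who give labor care, though the team that built the website recruits from the anesthesia service's patients and at least one member treats laboring women

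*Combined protocol and SAP*

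**What the plan says.** On who has a stake in the result, section 2.2 states: "The investigators created the website under review, and intend to test its effect on patient satisfaction". Section 1.2 gives the expected direction, which is greater satisfaction with website access.

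On where participants come from, section 21.3 says that Obstetrics notifies Anesthesiology of women expected to labor, "in order for them to provide possible consultation and appropriate pain relief care". It then says: "The study team will identify potential participants from among this patient population".

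On who is in contact with them, section 16.1 says that a named member of the team "regularly treats laboring women as part of her routine clinical duties". Section 23.1 adds: "Investigators who will conduct recruitment and consent are already authorized for patient contact in this situation". Section 23.3 adds: "The PI is already authorized to contact these patients and review their records as part of medical practice".

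On how the arm could become known, section 9.2 randomizes women to usual care, or to usual care plus an hour with the website on an iPad from the Anesthesiology department. Section 19.1 places this in the Labor & Delivery areas. Section 11.3 says: "Investigators may notify one another of recent enrollments by use of the" secure email function or a hospital messaging system. It does not say whether such a notice may contain the arm.

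On the arms being alike, section 14.1 begins "The only difference between study arms is the" availability of the website. Sections 14.3, 16.1 and 20.2 say that the study changes no clinical decision.

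**The concern.** A two-arm comparison credits any systematic difference in the outcome to the intervention. That is justified only if the arms are otherwise handled alike from randomization to survey. Satisfaction with labor and pain relief plausibly responds to how long the anesthesia clinician stays, how fully she explains and how quickly she comes. Section 2.1 itself says that factors beyond pain relief shape the childbirth experience.

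In this plan, people who made the product and predict its success may be among those giving that care, and may know who had the product. If knowing the arm changes their manner, even without intent, the Wilcoxon-Mann-Whitney test in section 11.1 counts the result as a website effect. As written, the plan also collects nothing that would show afterwards whether this happened.

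The point concerns care between randomization and delivery. Concealment of the sequence before enrollment and the way the survey is given are separate matters.

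**Working it through.** **Step 1: does any passage close the route?**

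- Section 9.2 describes randomization and the iPad session. It does not say who reveals the assignment, and it describes no masking of staff.
- Section 11.3 covers the security of messages between investigators and is silent on the arm.
- Section 14.1 says that website availability is the only difference between arms.
- Sections 14.3, 16.1 and 20.2 say that clinical decisions are not modified. These are statements of intent with no procedure or check behind them. They also concern decisions, not time, explanation or promptness.

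So the route is open. The documents say nothing about how often it would be used.

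**Step 2: the plan's own figure.** Inputs are alpha 0.05, 80% power, about 100 completed surveys and a detectable difference of about 58% of the SD (4.2, 4.3), with a Wilcoxon-Mann-Whitney test (11.1). The allocation ratio and sidedness are not stated. I assume 1:1, so 50 per arm, and a two-sided test. The Wilcoxon efficiency relative to the t-test, for normal data, is 3/π = 0.955.

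Normal approximation: (1.960 + 0.842) × √(2 / (50 × 0.955)) = 0.573 SD. The t-based calculation with the same effective sample size gives 0.579 SD. The stated 58% reproduces, so the sample size is not in question here.

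**Step 3: illustration of a bias.** Let b be the net shift in satisfaction toward the website, in SD, that comes only from arm-aware care, with no true website effect. With n = 50 per arm:

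- δ = b × √(n/2) × √(3/π) = b × 5 × 0.977
- P(reject) = Φ(−1.96 − δ) + 1 − Φ(1.96 − δ)

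| b (SD) | δ | Lower tail | Upper tail | P(reject) |
|---|---|---|---|---|
| 0 | 0 | 0.0250 | 0.0250 | 5.0% |
| 0.04 | 0.195 | 0.0156 | 0.0388 | 5.4% |
| 0.10 | 0.489 | 0.0072 | 0.0706 | 7.8% |
| 0.20 | 0.977 | 0.0017 | 0.1629 | 16.5% |

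One way to reach these values is to suppose that arm-aware investigator care adds 0.4 SD for the intervention women who receive it. Then b = share treated × 0.4:

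- 10% treated gives 0.04 SD
- 25% treated gives 0.10 SD
- 50% treated gives 0.20 SD

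Both the share and the 0.4 SD are assumptions, since the documents give neither. An effect of 0.4 SD is not small: it is 0.4/0.58 = 69% of the difference the trial is sized to detect.

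**Step 4: does a larger sample help?** Section 4.2 allows up to 150 surveys. At 75 per arm, √(75/2) = 6.124 replaces 5 in the formula. The rates for b = 0.10 and 0.20 become 9.2% and 22.3%. More surveys do not remove a bias; they make it likelier to be declared significant.

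**The case against.** The strongest reply is that a reader might infer that the website's creators, as a group, treat the women they enroll and share the arm among themselves. The documents do not support that. Routine treatment of laboring women is stated for one person (16.1). The team also includes medical students (20.1, 20.3). No section says that an investigator will treat an enrolled woman. Section 23.1 is a privacy statement about permitted contact, not an assignment of care, and 20.3 says a named team member has nonclinical time for such projects. Section 11.3 mentions notices of enrollment, not of arm. All of this stands. It limits the point to an open route.

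The size is also open to challenge. With thousands of parturients a year at the hospital (20.3), the share treated by one investigator could be low, and at 0.04 SD the rejection rate is close to nominal. The bias could also run the other way if controls received extra explanation to make up for not having the website. Both objections stand, so no particular rejection rate can be claimed.

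A woman who has read the website may ask more and be told more. In a comparison with usual care, that is part of the website's effect and should be left alone. Only staff behavior prompted by knowing the arm is at issue.

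Finally, participants cannot be masked and they report the outcome themselves, so expectation effects would remain with perfectly masked clinicians. That is true, but clinician awareness is a distinct source and can be reduced at little cost. The statements that no clinical decision is modified do not answer the point, because nothing enforces or checks them.

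**Conclusion.** The concern holds as a gap in protection. People with a stake in the website recruit from the anesthesia service's patients, at least one of them treats laboring women, and no step keeps the arm from treating clinicians. The equality of care that 14.1 relies on is therefore asserted, not secured.

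The documents do not establish that care will differ, by how much or in which direction. Under the assumptions of 50 per arm, a two-sided 5% test, efficiency 3/π and no true effect, the illustrative rejection rate runs from 5.0% with no bias to about 16.5% at 0.20 SD toward the website. It is about 5.4% if only a tenth of intervention women are affected by 0.4 SD. This is an inexpensive improvement to make before enrollment. It does not invalidate the design.

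**What to change.** Amend sections 9.2 and 11.3 as follows.

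1. Where feasible, a study team member who is not giving that woman's labor care reveals the assignment, hands over the iPad and collects it. The arm is not disclosed to the physician investigator while on clinical duty, or to other treating staff.
2. Enrollment notices between investigators never state the arm.
3. Two fields are recorded for each woman: whether an investigator gave her labor analgesia consultation or care, and whether that person knew the arm. Both are reported descriptively by arm.
4. All randomized women with surveys stay in the main comparison.

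Two additions may suggest themselves and should be left out. Repeating the comparison without women treated by an arm-aware investigator would select on something that arises after randomization. Awareness is likelier in the iPad arm, so the exclusion could itself create bias. Extra study visits for controls would change the usual-care comparator set in 9.2.

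The cost is a few sentences of protocol text and two short fields per woman. No change in sample size or in the main test is needed. Masking will be imperfect, because the iPad is visible on the unit and women may mention it, and the participants themselves remain unmasked. The *where feasible* wording matters because the team is small and the PI is the only investigator stated to speak some Spanish (section on non-English-speaking subjects).
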